### **10.2.1.2 Adverse Events by System Organ Class and Preferred Term**

The number and percentage of subjects experiencing adverse events will be tabulated by SOC and MedDRA PT by "as treated" treatment group and overall. The SOCs will be presented in alphabetical order, and the PTs will be presented in alphabetical order within each SOC.

The following summaries of adverse events will be generated:

- All TEAEs
- Treatment-emergent serious adverse events (SAEs)
- Treatment-emergent severe adverse events
- TEAEs reasonably possibly related to study drug
- TEAEs leading to discontinuation of study drug
- TEAE leading to death
- Frequent AEs (reported in 2% of subjects or more in any treatment group)

Subjects reporting more than one adverse event for a given MedDRA preferred term will be counted only once for that term (most severe incident for the severity tables and most related incident for the relationship tables). Subjects reporting more than one type of adverse event within a SOC will be counted only once for that SOC. Subjects reporting more than one type of adverse event will be counted only once in the overall total.

As a sensitivity analysis, the AE summary by SOC and PT will be repeated by randomized treatment groups (Upadacitinib 15 mg QD, Upadacitinib 30 mg QD and the combined placebo groups). In this summary, all AEs with an onset date after the first dose of study drug will be included, regardless of whether the AE occurred more than 30 days after the last dose of study drug.

### **10.2.1.3 TEAEs by Maximum Severity**

TEAEs will also be summarized by maximum severity by "as treated" treatment group and overall. If a subject has an AE with an unknown severity, then the subject will be

counted in the severity category of unknown, even if the subject has another occurrence of the same event with a severity present. The only exception is that if the subject has another occurrence of the same AE with the most extreme severity – severe. In this case, the subject will be counted under the severe category.

#### **10.2.1.4 TEAEs by Relationship**

TEAEs will also be summarized by relationship to Upadacitinib and Placebo, as assessed by the investigator, by "as treated" treatment group and overall. If a subject has a TEAE with an unknown relationship, then the subject will be counted in the relationship category of "unknown," even if the subject has another occurrence of the same event with a relationship present. The only exception is if the subject has another occurrence of the same TEAE with a relationship assessment of "reasonable possibility." In this case, the subject will be counted under the "reasonable possibility" category.

#### **10.2.1.5 Frequent ( $\geq 2\%$ ) Adverse Events and Reasonably Possibly Related Adverse Events by System Organ Class and Preferred Term**

TEAEs and reasonably possibly related AEs occurring for more than 2% of the subjects in any of the "as treated" treatment groups will be summarized by MedDRA PT in decreasing frequency separately.

#### **10.2.1.6 Adverse Events of Special Interest**

The Adverse Events of Special Interest (AESI) categories will be summarized and presented by "as treated" treatment group and overall using SOC and MedDRA PT. The AESI categories will be identified by the following search criteria per Standard MedDRA Queries (SMQs)/Company MedDRA Queries (CMQs) in [Table 8](#) below. Adjudicated cardiovascular events will be summarized and presented by treatment group using the CAC adjudicated categories.

**Table 8. AESI for Upadacitinib with SMQs/CMQs/PTs Searches**

AESI	Type of MedDRA Query	Broad or Narrow Search	SMQ/CMQ Search Criteria
Serious Infections	CMQ		"Infections" – Subset for SAEs
Opportunistic Infection excluding Tuberculosis and Herpes Zoster	CMQ		"Opportunistic Infection excluding Tuberculosis and Herpes Zoster"
Possible Malignancy	SMQ	Narrow	"Malignancies"
Malignancy	SMQ		"Malignant tumours"
Non-Melanoma Skin Cancer (NMSC)	SMQ	Narrow	Skin Malignant tumours (Narrow SMQ) removing Melanoma CMQ
Malignancy excluding NMSC			"Malignant tumours" SMQ removing NMSC output
Lymphoma	SMQ		"Malignant Lymphomas"
Hepatic Disorder	SMQ	Narrow	"Drug Related Hepatic Disorders"
Adjudicated Gastrointestinal Perforations	Output from adjudication		
Anemia	CMQ		"Non-Hemolytic and Non-Aplastic Anemias"
Neutropenia	CMQ		"Hematological Toxicity – Neutropenia"
Lymphopenia	CMQ		"Hematological Toxicity – Lymphopenia"
Herpes Zoster	CMQ		"Herpes Zoster"
Creatine Phosphokinase (CPK) Elevation	PT		Search only for the PT of "Blood creatine phosphokinase increased"
Renal Dysfunction	SMQ	Narrow	"Acute Renal, Failure"
Active Tuberculosis	CMQ		"Active Tuberculosis"
Adjudicated Cardiovascular Events	Output from CAC		
MACE*			
Cardiovascular Death			
Non-fatal Myocardial Infarction			
Non-fatal Stroke			

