### **6.1.1.3 Adverse Events of Special Interest**

The following AEs of special interest will be monitored during the study (see detailed toxicity management in Section 6.1.7):

- Serious infections
- Opportunistic infections
- Herpes zoster
- Active tuberculosis
- Malignancy (all types)
- Adjudicated gastrointestinal perforations

- Adjudicated cardiovascular events (e.g., major adverse cardiovascular event [MACE])
- Anemia
- Neutropenia
- Lymphopenia
- Increased serum creatinine and renal dysfunction
- Hepatic events and increased hepatic transaminases
- Elevated creatine phosphokinase (CPK)
- Adjudicated embolic and thrombotic events (non-cardiac, non-CNS).

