
**Table 4. Specific Toxicity Management Guidelines for Abnormal Laboratory Values (Continued)**

Laboratory Parameter	Toxicity Management Guideline
Serum Creatinine	
 
If serum creatinine is <math>> 1.5 \times</math> the baseline value and <math>> \text{ULN}</math>, repeat the test for serum creatinine (with subject in an euvoletic state) to confirm the results. If the results of the repeat testing still meet this criterion then interrupt study drug and re-start study drug once serum creatinine returns to <math>\leq 1.5 \times</math> baseline value and <math>\leq \text{ULN}</math>.
 
If confirmed serum creatinine <math>\geq 2 \text{ mg/dL}</math>, interrupt study drug and re-start study drug once serum creatinine returns to normal reference range or its baseline value.
 
 
For the above serum creatinine elevation scenarios, complete supplemental renal eCRF.

Creatine Phosphokinase	
 
If confirmed CPK <math>\geq 4 \times \text{ULN}</math>, and there are no symptoms suggestive of myositis or rhabdomyolysis subjects may continue study drug at the investigator's discretion.
 
If CPK <math>\geq 4 \times \text{ULN}</math> accompanied by symptoms suggestive of myositis or rhabdomyolysis, interrupt study drug and inform AbbVie Therapeutic Area Medical Director.
 
 
For the above CPK elevation scenarios, complete supplemental CPK eCRF.

For allowed study drug interruption, the following rules apply:

#### Period 1

- Allow study drug interruption up to 7 consecutive days for AEs and emergency surgery. Elective surgery will not be allowed during this 24-week period.
- If the subject must undergo emergency surgery, the study drug should be interrupted at the time of the surgery. After emergency surgery, allow reintroduction of study drug once the physician has examined the surgical site and determined that it has healed and there is no sign of infection.

#### Period 2

- Allow study drug interruption up to 30 consecutive days. The Investigator will make determination if study drug should be restarted for interruptions  $> 30$  days.
- If the subject undergoes elective surgery, the study drug should be interrupted 1 week prior to the planned surgery. Allow reintroduction of study drug once

the physician has examined the surgical site and determined that it has healed and there is no sign of infection.

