### **10.3.2.3 Assessment of Potentially Clinical Significant Laboratory Values**

The criteria for potentially clinically significant laboratory values will be determined by OMERACT criteria of Grade 3 or 4. For creatine phosphokinase and creatinine, NCI CTC criteria will be used.

The number and percentage of subjects meeting the criteria for potentially clinically significant laboratory values will be summarized by "as treated" treatment group and overall. Comparisons of the percentage of subjects experiencing a value meeting the criteria between treatment groups will be performed using Fisher's exact tests. Only p-values  $\leq 0.100$  when rounded to three digits will be presented.

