### **10.3.3.2 Assessment of Potentially Clinically Significant Laboratory Values**

Long-term laboratory data will be summarized based on the number and percentage of subjects meeting the criteria for potentially clinically significant laboratory values and by the actual treatment received at the time of the event occurrence. Starting with Amendment 4, all subjects will receive open-label upadacitinib 15 mg QD, including those currently on upadacitinib 30 mg QD. The treatment groups for summarizing potentially clinically significant laboratory values are the same as the ones for long-term AE analysis as described in Section 8.1 and Section 10.2.2. A subject can be counted under different treatment groups if he/she switched treatment and experienced potentially clinically significant laboratory values under different treatment groups.

In the evaluation of potentially clinically significant laboratory values, the baseline value will be determined by the last non-missing measurement recorded on or before the date of the first dose of study drug in the corresponding treatment group (which may be different than the first dose of study drug received in the study). For example, for a subject who started on Placebo and switched to Upadacitinib 15 mg QD, lab values under Upadacitinib 15 mg QD exposure would be evaluated against the baseline value defined as the last non-missing measurement recorded on or before the date of the first dose of Upadacitinib 15 mg QD. For subjects who switched from upadacitinib 30 mg QD to upadacitinib 15 mg QD, lab values under upadacitinib 15 mg QD exposure would still be evaluated against the baseline defined based on the first dose of Upadacitinib 30 mg QD.

A listing of all subjects with any laboratory determination meeting OMERACT criteria of Grade 3 or 4 will be provided by Grade. For creatine phosphokinase and creatinine, NCI CTC criteria will be used. For each of these subjects, the whole course of the respective parameter will be listed.

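### SAP Table 8 has no creatinine term for a renal AESI that includes increased creatinine, and the long-term laboratory counts miss drug-interrupting rises below Grade 3

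*SAP*

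**What the plan says.** - **AESI definition.** Protocol 6.1.1.3 has a single renal entry: "Increased serum creatinine and renal dysfunction".
- **AESI search.** The matching row of SAP Table 8 is "Renal Dysfunction", a narrow standard MedDRA query (SMQ) entered as "Acute Renal, Failure". No row names creatinine. By contrast, CPK elevation has its own preferred-term search, and anemia, neutropenia and lymphopenia each have a company query.
- **Interruption criteria.** Protocol Table 4 gives two, each requiring confirmation: creatinine above 1.5 x baseline and above ULN, or creatinine of at least 2 mg/dL. It adds: "For the above serum creatinine elevation scenarios, complete supplemental renal eCRF".
- **Laboratory count.** SAP 10.3.2.3 states: "The criteria for potentially clinically significant laboratory values will be determined by OMERACT criteria of Grade 3 or 4". NCI CTC grades replace OMERACT grades for creatinine. SAP 10.3.3.2 counts potentially clinically significant values over the long term and adds: "A listing of all subjects with any laboratory determination meeting OMERACT criteria of Grade 3 or 4 will be provided by Grade".
- **Shift tables.** SAP 10.3.2.2 plans them for the Week 12 analysis. SAP 10.3.3, the long-term section, has none. Protocol 8.1.5.1 plans laboratory shifts within safety analyses that cover Period 1 alone and both periods combined.
- **What is still open.** SAP 11.1 says Period 1 reporting is complete and that version 3.0 governs only future long-term reporting.

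**The concern.** The protocol treats a creatinine rise as part of the renal AESI, yet the SAP's only route into that category is a query named for renal failure. A creatinine adverse event outside the query's terms would not enter the AESI rate per 100 patient-years (SAP 10.2.2.3) or the AESI difference from placebo (SAP 10.2.2.1).

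The laboratory tables might be expected to act as a backstop, but their threshold is well above the one at which the protocol interrupts drug. Over up to 260 weeks, a subject could meet a protocol interruption criterion and have a renal form completed without entering any planned long-term laboratory count.

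**Working it through.** The plan states no figure on this point, so there is none to reproduce. The check compares thresholds and then lists the outputs.

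**1. Inputs.** Let c be creatinine, b baseline and U the ULN, in mg/dL.
- T1 (Protocol Table 4): c > 1.5b and c > U, confirmed.
- T2 (Protocol Table 4): c ≥ 2, confirmed.
- Grade 2 (SAP Appendix A footnote): above 1.5 and up to 3.0 times b or U.
- Grade 3 (same footnote): c > 3b, or c > 3U up to 6U. Grade 4: c > 6U.

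I take either multiple as sufficient for Grade 3. That makes Grade 3 as easy as possible to reach, and so makes the gap as small as possible.

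**2. The gap in general.**
- T1: interrupted but below Grade 3 when max(1.5b, U) < c ≤ min(3b, 3U). This range is non-empty when 1.5b < 3U and U < 3b, that is, when U/3 < b < 2U.
- T2: interrupted but below Grade 3 when 2 ≤ c ≤ min(3b, 3U). This is non-empty when b and U are both at least 2/3 = 0.67.

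A T1 value in the gap exceeds 1.5b, so it is Grade 2. A T2 value can be Grade 1: with b = 1.5 and U = 1.4, 2/1.5 = 1.33 and 2/1.4 = 1.43.

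**3. Illustrations.** The documents give neither b nor U. The values are assumed, from b = 0.5 to 1.5 and U = 1.0 to 1.4.

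| b | U | Interrupts | Grade 3 | Uncounted |
|---|---|---|---|---|
| 0.5 | 1.4 | above max(0.75, 1.40) = 1.40 | above min(1.50, 4.20) = 1.50 | above 1.40 to 1.50 |
| 0.8 | 1.2 | above max(1.20, 1.20) = 1.20 | above min(2.40, 3.60) = 2.40 | above 1.20 to 2.40 |
| 1.0 | 1.2 | above max(1.50, 1.20) = 1.50 | above min(3.00, 3.60) = 3.00 | above 1.50 to 3.00 |
| 1.5 | 1.2 | from 2.00 (T2; T1 needs above 2.25) | above min(4.50, 3.60) = 3.60 | 2.00 to 3.60 |

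The gap is present at every pair in the assumed range. Its width depends strongly on baseline.

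**4. Where a rise below Grade 3 would appear.**
- Week 12 analysis: shift tables by grade (SAP 10.3.2.2) and mean change with an ANOVA test (SAP 10.3.2.1).
- Long-term analysis: mean change by visit only (SAP 10.3.3.1). There is no subject count, no listing and no shift table.
- If reported as an adverse event: preferred-term rates per 100 patient-years (SAP 10.2.2.2), and the renal AESI only if the query contains the reported term.
- Supplemental renal eCRF: the SAP states no analysis of it.

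**5. Scale.** Under SAP 8.1 each long-term dose group includes placebo switchers, so the planned size is 150 + 75 = 225 per dose. One uncounted subject is 1/225 = 0.44 percentage points of such a group. The documents give no rate of creatinine rises, so the number of subjects cannot be derived.

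**The case against.** A reader might infer four stronger things, none of which the documents support.

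- **That creatinine events are excluded from the renal AESI and its rate is understated.** The SMQ's term list is not in the documents. Some or all such events may be captured, so the defect is lack of assurance.
- **That all interrupting rises escape the laboratory count.** Those above 3 x baseline or 3 x ULN are Grade 3 or 4 and are counted.
- **That an interrupting rise is itself an AESI.** Under Protocol 6.1.1.1 a laboratory abnormality is an adverse event only if it leads to discontinuation, needs therapeutic intervention, or is judged one by the investigator. Interruption alone does not qualify, so a preferred-term row would not reach every case and a laboratory count is needed as well.
- **That creatinine is otherwise invisible.** Step 4 of the working shows several outputs that carry it.

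The best defence of Table 8 is that Protocol 6.1.1.3 is a monitoring list, while the AESI list for analysis in Protocol 8.1.5.2.1 names renal dysfunction and increased CPK but not creatinine. Table 8 follows that split, and SAP 11.1 says it was aligned with a product-level plan. This explains the omission. It does not settle it, because the list in 8.1.5.2.1 is expressly not exhaustive and so does not displace 6.1.1.3. The SAP's allowance for additional adverse event tabulations commits to nothing on creatinine. The protocol's plan for shifts over both periods also stands, but the SAP's long-term section does not carry it out.

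**Conclusion.** The point holds in two limited parts. First, the SAP does not assure that adverse events of increased creatinine, which Protocol 6.1.1.3 places within the renal AESI, are found by the renal AESI search. Second, confirmed creatinine values that meet a Protocol Table 4 interruption criterion but stay at or below 3 x baseline and 3 x ULN fall outside the long-term potentially clinically significant count, and no long-term shift table shows them.

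The second part follows from the documents' own thresholds whenever U/3 < b < 2U for the first criterion, or b and U are both at least 0.67 mg/dL for the second. The milligram ranges rest on assumed baselines and ULNs. No understatement of the renal AESI rate is shown, and its size cannot be derived. The Week 12 analysis is complete, its shift tables show Grade 2 rises, and it needs no change. This is a minor reporting improvement.

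**What to change.** For the long-term reporting still to come:

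1. **SAP Table 8:** add a row for increased serum creatinine, with a preferred-term search for *Blood creatinine increased*, beside the existing renal row and in the style of the CPK row. Report it in the AESI rates per 100 patient-years.
2. **SAP 10.3.3.2:** add a count by treatment group of subjects meeting either Protocol Table 4 creatinine criterion: confirmed above 1.5 x baseline and above ULN, or confirmed at least 2 mg/dL. State which baseline applies, because 10.3.3.2 resets it at the first upadacitinib dose for subjects who began on placebo.

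The cost is one AESI row and one laboratory row, from data already collected. No clinical rule changes. The downside is one AESI row beyond the product-level list.

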**Table 8. AESI for Upadacitinib with SMQs/CMQs/PTs Searches (Continued)**

AESI	Type of MedDRA Query	Broad or Narrow Search	SMQ/CMQ Search Criteria
Undetermined/Unknown Cause of Deaths			
Other Cardiovascular events			
Adjudicated Thrombotic Events	Output From CAC		
Venous Thromboembolic Events**			
Deep Vein Thrombosis			
Pulmonary Embolism			
Other Venous Thrombosis			
Arterial Thromboembolic Events (non-cardiac, non-neurologic)			

CAC = Cardiovascular Adjudication Committee; CMQ = company MedDRA query; PT = preferred term; SMQ = standard MedDRA query

\* MACE; Major Adverse Cardiovascular Events, defined as cardiovascular death, non-fatal myocardial infarction and non-fatal stroke.

\*\* Venous thromboembolic events (VTE) include deep vein thrombosis (DVT) and pulmonary embolism (PE) (fatal and non-fatal).

Additional AEs may be considered for tabulation/summary based on recommendations from Clinical and Safety as deemed appropriate.

### 10.2.2 Analysis of Long-Term Adverse Event Rates

Long-term adverse event rates will be analyzed using event rates adjusted by cumulative exposure and will be based on the actual treatment received at the time of AE occurrence. Starting with Amendment 4, all subjects will receive open-label upadacitinib 15 mg QD, including those currently on upadacitinib 30 mg QD. For subjects who previously received upadacitinib 30 mg QD, adverse events and exposure to upadacitinib 30 mg QD will be censored at the time of dose switch; subsequent adverse events and exposure

starting the day of first dose of upadacitinib 15 mg QD will be summarized under a separate group. The detailed treatment groups, including the handling of dose switch, are described in Section 8.1.

#### **10.2.2.1 Overview of Adverse Events Rates per 100 Patient-Years of Study Drug Exposure**

An overview of AEs per 100 patient-years of study exposure will be presented by treatment group and overall for the following AE categories.

- All TEAEs
- Treatment-emergent serious adverse events (SAEs)
- Treatment-emergent severe adverse events
- TEAEs reasonably possibly related to study drug
- TEAEs of special interest
- TEAEs leading to discontinuation of study drug
- TEAE leading to death

For this calculation, 1 year will be considered to be 365.25 days. For each treatment group, the numerator of the overall rate will be the total number of TEAEs reported for the event; that is, a subject can contribute more than one event to the numerator. For each treatment group, the denominator of the rates will be the total number of days exposed to study drug summed across all treated subjects divided by 365.25. Please refer to Section 6.0 for the calculation of study drug exposure. The AE rate per 100 patient-years of exposure will be calculated as  $([\text{numerator}/\text{denominator}]) * 100$ . The number of AEs reported (numerator), the total number of years of study drug exposure (denominator), and the AE rate per 100 patient-years will be presented for each treatment group and overall.

In the AE overview summary, any event with an unknown severity will be considered as severe and any AE with an unknown relationship will be considered as having "reasonable possibility" of being related to study drug.

Additional AEs may be considered for tabulation/summary based on recommendations from Clinical and Safety as deemed appropriate.

For TEAEs of special interest, the point estimate and 95% CI (using normal approximation) will be provided for the treatment difference in AE rate per 100 patient-years between each Upadacitinib dose group and the combined placebo group.

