#### **8.1.5.2.1 Treatment-Emergent Adverse Events (TEAE)**

AEs will be coded using MedDRA. A TEAE is defined as AE that began or worsened in severity after initiation of study drug.

AEs starting more than 30 days following the last dose of study drug will not be included in summaries of TEAEs. For subjects who continued into Period 2, AEs that are reported in Period 2 will be captured in the combined safety analysis of Period 1 and Period 2.

As a general safety summary, the number and percentage of subjects experiencing TEAEs will be summarized for each treatment group for the following AE categories:

- All AEs;
- All severe AEs;
- All reasonably possibly related AEs;
- All SAEs;
- Frequent AEs (reported in 2% of subjects or more in any treatment group);
- Frequent reasonably possibly related AEs (reported in 5% of subjects or more in any treatment group);
- Discontinuations due to AEs;
- Death.

Additional AEs may be considered for tabulation/summary based on recommendations from Clinical and Safety as deemed appropriate.

TEAEs will be summarized and presented by system organ classes (SOCs) and preferred terms (PTs) using MedDRA. The SOC's will be presented in alphabetical order, and the PTs will be presented in alphabetical order within each SOC.

TEAE will also be summarized by maximum severity and by maximum relationship.

The AEs of special interest (including but not limited to serious infection, opportunistic infection, herpes zoster, TB, gastrointestinal perforations, malignancies, MACE, renal

dysfunction, anemia, increased CPK, and drug-related hepatic disorders) will be summarized. Event rate (per 100 patient years) for AEs of special interest will also be summarized for the combined safety analysis of Period 1 and Period 2.

All AEs leading to discontinuation of study drug will be presented in listing format. A listing by treatment group of TEAEs grouped by SOC and MedDRA preferred term with subject identification numbers will be generated.

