## **10.2 Analysis of Adverse Events**

A treatment-emergent Adverse Event (TEAE) is defined as an adverse event with an onset date that is after the first dose of study drug, and no more than 30 days of the drug after the last dose of study drug.

Events where the onset date is the same as the study drug start date are assumed to be treatment-emergent, unless the study drug start time and the adverse event start time are collected and the adverse event start time is prior to the study drug start time. If an incomplete onset date was collected for an adverse event, the event will be assumed to be treatment-emergent unless there is other evidence that confirms that the event was not treatment-emergent (e.g., the event end date was prior to the study drug start date).

Adverse event data will be presented by SOCs and PTs using MedDRA Version 19.1 or most up to date version. All adverse event tables will be sorted in alphabetical order by SOC and PT and descending percentages for each treatment group.

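### Long-term adverse event rates count events for 30 days after the last dose but divide only by days on drug, so they are biased upward, unevenly, wherever subjects stop treatment

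*SAP*

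**What the plan says.** **Numerator.** SAP 10.2 treats an event as treatment-emergent if it starts after the first dose "and no more than 30 days of the drug after the last dose of study drug". Protocol 8.1.5.2.1 sets the same limit: "AEs starting more than 30 days following the last dose of study drug will not be included in summaries of TEAEs". In SAP 10.2.2.1, "the numerator of the overall rate will be the total number of TEAEs reported for the event", and one subject may contribute several events.

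**Denominator.** The same section says that "the denominator of the rates will be the total number of days exposed to study drug summed across all treated subjects divided by 365.25". Sections 10.2.2.2 and 10.2.2.3 use this denominator for the rates by system organ class and preferred term and for the events of special interest. None of them mentions post-dose time.

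**Exposure formula.** All three sections give a pointer: "Please refer to Section 6.0 for the calculation of study drug exposure". Section 6.0 covers demographics, medical history and concomitant medication. Exposure is in Section 8.1, which defines the exposure groups but gives no day-count rule.

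**Attribution.** SAP 10.2.2 says that the rates "will be based on the actual treatment received at the time of AE occurrence". For subjects who had been on 30 mg, "adverse events and exposure to upadacitinib 30 mg QD will be censored at the time of dose switch", and what follows goes to a separate group.

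**Comparison.** For events of special interest, SAP 10.2.2.1 plans a rate difference with a 95% confidence interval between each upadacitinib dose group and combined placebo.

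**The concern.** A subject who stops study drug has up to 30 further days in which a new event counts and no person-time accrues. The result is not events per unit of time at risk.

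The mismatch differs by group. A subject who moves from placebo to active drug at Week 12, or from 30 mg to 15 mg, has not had a last dose of study drug. That subject leaves no tail in the group just left, because later events and later days both go to the next group. At final reporting, by contrast, treatment for everyone in the 15 mg and 15 mg-after-30 mg groups ends with a last dose. Exposure after the switch is also shorter, so a fixed 30 days weighs more there. Unequal upward bias does not cancel in a between-group difference.

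**Working it through.** The documents state no event rate, exposure total or size for this effect, so there is no figure to reproduce. The check is person-time arithmetic.

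**Inputs from the documents**
- Tail: up to 30 days after the last dose (SAP 10.2). Protocol 6.1.4 collects adverse events for those 30 days, so tail events can reach the numerator.
- Maximum treatment: 260 weeks = 1820 days (Protocol synopsis).
- Randomised: 150 to 15 mg, 150 to 30 mg and 75 + 75 to placebo, with placebo lasting 12 weeks = 84 days (SAP 4.2). Each continuous active group is therefore 150 + 75 = 225 subjects. The 75 who start at Week 12 have at most 1820 − 84 = 1736 days.
- Planned dropout: 10% (SAP 4.3).

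**Assumed, because the documents do not say:** long-term discontinuation of 0 to 20% per year at a constant hazard h; mean post-switch exposure of 1 to 2 years; a full 30-day tail; and equal event rates in the tail and on drug (ratio r = 1).

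**Formula.** Let s be the share of subjects with a tail and m the mean on-drug days per subject. Then

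excess = r × s × 30 / m.

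With r = 1 this is the excess of the planned rate over the matched-window rate.

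**15 mg, final reporting (s = 1)**
- Floor: m cannot exceed 1820, so the excess is at least 30/1820 = 1.6%.
- All complete: m = (150 × 1820 + 75 × 1736)/225 = 1792, and 30/1792 = 1.7%.
- With a constant hazard, mean exposure over L years is (1 − exp(−hL))/h. At 10% per year m = 1416 days, giving 2.1%. At 20% per year m = 1142 days, giving 2.6%.

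**15 mg after 30 mg (s = 1)**
- Mean of 52 weeks: 30/364 = 8.2%.
- Mean of 78 weeks: 30/546 = 5.5%.
- Mean of 104 weeks: 30/728 = 4.1%.

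**30 mg (tail only if the subject stops before the switch)**
With a constant hazard the number of stops per on-drug year is h, whenever the switch falls. The excess is therefore h × 30/365.25: 0% at h = 0, 0.4% at 5%, 0.8% at 10% and 1.6% at 20% per year.

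**Placebo (tail only for those who stop before Week 12, on average at day 42)**
- 10% stop: on-drug days = 150 × (0.9 × 84 + 0.1 × 42) = 11,970; tail = 15 × 30 = 450; 450/11,970 = 3.8%.
- 20% stop: 900/11,340 = 7.9%. None stop: 0%.

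**Sensitivity to r.** At m = 1792, r = 0.5 gives 0.8% and r = 2 gives 3.3%.

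**Effect on the planned contrast.** Suppose two groups share a true rate R.
- 15 mg with all completing, against placebo with 10% dropout: (1.017 − 1.038)R = −0.021R.
- 30 mg at 10% per year, against the same placebo: (1.008 − 1.038)R = −0.030R.
- 15 mg against placebo with no dropout: +0.017R.

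The bias in the difference is a few per cent of R, and its sign is not fixed.

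**The case against.** The case against has real substance.

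- **The measure is openly labelled.** The section titles name study drug exposure as the base, and the number of events, the years and the rate are all displayed. This stands as a point about transparency. It does not make the two windows agree.
- **Adding off-drug days has its own cost.** If the event rate falls after stopping, the longer denominator dilutes the on-treatment rate, and the new rates will not match earlier tables. Both points stand, and both are met by showing the two denominators together.
- **The formula is unwritten.** Counting on-drug days only is the plain reading of the text, but no day-count rule confirms it. An event after the last dose also has no treatment at the time it occurs, so its group is not stated. This strengthens the case for a clarification.

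Two stronger readings are tempting.

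- **A reader might infer that every rate is inflated, by about 1% to 8%.** The documents do not support this. Subjects who switch, and subjects still on drug at a data cut, have no tail, so placebo and 30 mg can be near zero. An event that starts after the last dose can hardly have led to discontinuation, so that category is essentially untouched. The range itself needs exposure, stopping and event-rate assumptions that neither document gives. With mean post-switch exposure of 26 weeks, for example, the excess would be 30/182 = 16.5%. Full tails are also an upper bound: Protocol 5.1 makes the 30-day contact after withdrawal of consent depend on the subject's willingness.
- **A reader might infer that formal dose-to-dose or before-and-after-switch comparisons are biased.** SAP 10.2.2 plans none. Its only long-term contrast with an interval is against placebo, for events of special interest.

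**Conclusion.** The mismatch is in the text and holds on a plain reading: the numerator runs to 30 days past the last dose and the denominator stops at it. Rates are biased upward wherever subjects stop drug, by about s × 30 days / mean exposure if the tail is fully observed and r = 1.

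| Group | Approximate excess | Rests on |
|---|---|---|
| 15 mg, final reporting | 1.6–2.6% | floor from 260 weeks; upper end from 20% per year stopping |
| 15 mg after 30 mg | 4–8% | mean post-switch exposure of 1–2 years |
| 30 mg | 0–1.6% | 0–20% per year stopping before the switch |
| Placebo | 0–8% | 0–20% stopping before Week 12; 3.8% at the planned 10% |

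Only the 1.6% floor for 15 mg uses the documents' own durations alone, and it too needs a full tail and r = 1. The bias is small. With about 33 placebo patient-years (11,970/365.25), sampling error will usually dominate the differences from placebo. The point is minor, but it is systematic, differs by group and is easy to remove. SAP 11.1 confines version 3.0 to future long-term reporting, so the completed primary analysis is untouched.

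**What to change.** In SAP 10.2.2.1 to 10.2.2.3:

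1. Report the rates with matched windows. Define time at risk as days on treatment plus up to 30 days after the last dose, ended earlier at death, study exit, data cut or the first dose in the next treatment group.
2. Show the rate on the on-drug denominator alongside, for comparability with earlier tables.
3. Assign events that start after the last dose to the last treatment received.
4. Change the cross-reference from Section 6.0 to Section 8.1, and write the exposure day-count formula there.

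The cost is SAP wording, one derived variable and an extra column. Rates on the matched denominator will be slightly lower where subjects stop drug, and a footnote must explain why they differ from tables built on the on-drug denominator.
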